2. Bilateral splanchnic nerve block performed by an anesthesiologist (see images below) (CS). Following the right heart catheterization procedure the patient will be prone on the abdomen. Central venous access remains in place. Needle will be placed under fluoroscopic guidance in the posterior chest wall. Anesthetic solution (1% lidocaine with epinephrine) (1:200.000) will be injected (10-15 ml on each side). Patient will then be placed back on his/her back and central

hemodynamics are recorded again for the next 1-1.5 hours, approximately every 15 minutes. The central venous catheter will be removed after the hemodynamic monitoring is completed in the catheterization laboratory. Unless the primary team requested the catheter to remain in place and the patient is moved to the intensive care unit.

Following the block, the subject will repeat the positional change of a leg raise at 30, 60, and 90 minutes post-block to observe any changes in shortness of breath symptoms.

Additional measurements include:

- Orthostatic vitals will be obtained at the end of the hour while in the catheterization lab (CS).
- Dyspnea questionnaire (CS)
- If medically indicated a Swan Ganz catheter will be left in place. This would enable continuous monitoring of central hemodynamics for the next 24h (q4h) (SOC).

Follow up procedures:

Following right heart catheterization and lidocaine splanchnic nerve block the patient will be monitored on the floor/CCU for at least 48 hours following nerve block (SOC).

- Continuous recording of urine output for 24 hours (SOC). They will then be asked to void again 3 and 8 hours after the placement of the nerve block and 24 hours after nerve block (CS).
- Basic vitals (SOC) and orthostatic vitals (CS) within 24 hours after nerve block, and record heart rate variability using a non-invasive wrist monitor (CS).

- Repeat labs 12-24 hours after nerve block (next morning) [BUN (SOC), BMP (SOC) and pro-BNP (CS)
- Labs: Angiotensin 2, plasma metanephrines (if on inotropes), plasma catecholamines, vasopressin and urine sodium will be collected immediately before and after the procedure
- Dyspnea questionnaire at 12-24 hours after nerve block (CS) and again at 48 hours
- Six minute walk test (CS) within 24 hours after block and again at 48 hours
- Weight the next morning after nerve block (SOC) and at 48 hours.
- Echocardiogram within 1-2 hours after nerve block (CS)
- Positional change of bending over to evaluate 'bendopnea' (shortness of breath symptoms with bending over).

Phone Call

Subjects will be contacted by study team six months (\pm 14 days) following their nerve block procedure. The purpose of this call will be to obtain mortality status and document the number of inpatient admissions since the procedure.

Blood samples processing:

Some blood samples collected before and after the nerve block (plasma metanephrines, plasma catecholamines, angiotensin II and arginine vasopressin) will be processed (centrifuged) and stored at -70 degrees Fahrenheit before sent out to an external lab. Storage duration may vary between weeks to months. Samples will be stored in a research freezer located on the 7th floor of Duke North (cath lab research freezer). As part of the study, we will send blood for study-related laboratory tests to the Mayo clinic and Inter Science Institute. These would include laboratory tests such as metanephrines, vasopressin, catecholamines, and angiotensin.

Safety endpoints:

- The duration of the anesthetic block is estimated for 1.5 hours. The subject will be monitored for up to 1.5 hours in the catheterization laboratory (acute safety). Chronic safety up to 48 hours post procedure. Hereby the patient will be observed clinically on the floor or CCU per standard clinical care routine. Further the subject's medical chart will be observed for 6 months following study enrollment to evaluate for recurrent admissions for heart failure.

Incidence of major side effects like:

- Pneumothorax, possibly requiring a chest tube
- Aortic puncture with retroperitoneal bleed or hematothorax
- Spinal cord trauma with possibly paralysis

Incidence of minor side effects like:

- Orthostatic hypotension
- Pain at puncture site and intercostal neuralgia

- Gastrointestinal dysmotility including diarrhea, constipation and abdominal cramping
- Bleeding at puncture site

Efficacy endpoints:

The following efficacy endpoints will be evaluated:

- Primary: Reduction in central venous pressure and/or pulmonary artery pressure (diastolic) and/or pulmonary capillary wedge pressure at 30-60 minutes after nerve block
- Secondary: Increase in cardiac output, improvement in echocardiographic parameters like ejection fraction (increase), central venous pressure (decrease), pulmonary artery systolic pressure (decrease), right ventricular diameter (decrease), left ventricular diameter (decrease)
 - Reduction in pro brain natriuretic peptide (pro-BNP)
 - Increase in UOP (output measured in ml/hour) and renal function (BUN and creatinine) in the hours following the procedure. Follow up for 48hours
 - Symptomatic improvement like a decrease in dyspnea (dyspnea questionnaire) and 6-minute walk test

5. Selection of Subjects:

Subjects will be recruited from Duke University Medical Center. All potential study subjects are admitted for ADHF and are treated as inpatient on the regular floor or in the intensive care unit.

The study will enroll subjects who meet the criteria as detailed below. Potentially eligible patients will be consented and entered into a screening process, which will include a chart review and physical examination. The primary enrollment target is up to 20 subjects (10 HF with preserved ejection fraction and 10 HF with reduced ejection fraction).

Inclusion criteria:

- Age 18-90
- Established diagnosis of HFpEF or HFrEF
- Admitted to DUMC for decompensated HF (NYHA stage 3-4, Class C-D), including patients on inotropic medication
- Symptomatic with dyspnea with clinical, radiographic or echocardiographic signs of fluid overload
- Planned for elective diagnostic right (+/- left) heart catheterization
- On a stable HF drug regimen prior to admission
- Anticipated hospital stay of at least 2 nights following catheterization procedure

- Preferably "diuretic resistant". Urine output <50ml/hour in the 24 hours preceding enrollment into the study.

Exclusion criteria:

Contraindicated medications:

- Anticoagulation at the time the procedure or in case of recent warfarin use an INR >1.4. Anticoagulation includes: warfarin, or novel oral anticoagulants like dabigatran, rivaroxaban, apixaban, endoxaban or full dose intravenous heparin products or bivalirudin and fondaparinux). Antiplatelet agents besides aspirin such as ticagrelor, prasugrel, Plavix are also considered to be a contraindication if used at time point of procedure.
- Immunosuppressive medications for solid organ transplant

HF medication regimen:

- Initiation of HF medications (in the 48 hours preceding the study) such as beta blockers, ACEI, ARB, aldosterone receptor blockers, calcium channel blockers of any type, central sympatholytics like clonidine, moxonidine,

- Recent acute MI or hemodynamic instability:

- Acute MI (STEMI or Type I NSTEMI) within 7 days?
- Evidence of progressive cardiogenic shock within 48 hours
- Repeat systolic blood pressure <90mmHg or >180mmHg

Certain forms of HF:

- Restrictive cardiomyopathy
- Constrictive pericarditis
- Pericardial effusion with evidence of tamponade
- Severe valvular stenosis

Severe bleeding risk:

- Known history of an increased bleeding risk
- Thrombocytopenia (<50,000)

Significant comorbidities:

- End-stage renal disease CKD stage 5 due to primary renal pathology
- Any form of preceding acute or chronic use of ultrafiltration or hemodialysis
- History of thoracic spine surgery
- Scoliosis of the thoracic spine
- History of lung surgery or history of pneumothorax or chest tube placement during the current admission
- History of lung disease other than asthma and COPD (like interstitial fibrosis, cystic fibrosis, pneumonitis, lung cancer etc.)
- Respiratory instability (dependent on >4 L nasal cannula for a saturation >90% SpO2)
- Exclude severe pulmonary hypertension
- History of abdominal organ transplant (liver, pancreases, small bowel, kidney) or splenectomy

Pregnancy

Procedure

- Unable to tolerate procedure as determined by patient or investigator

- Patient will be excluded if invasive hemodynamics on study date determine that the patient does not have elevated filling pressures. Following pressures/situations will exclude the patient: wedge pressure <15mmHg (<12mmHg on inotrope) and greater than the central venous pressure or patient determined by study personnel to be at risk for nerve block related complications.

6. Subject Recruitment & Compensation:

Potential subjects will be identified via two potential pathways. Cardiology inpatient teams will be informed about the study and will be encouraged to notify the study team if a patient is planned for an elective right (+/-) left heart catheterization in the upcoming days. Subjects will also be identified by a daily review of the catheterization scheduling board, which identifies scheduled procedures for the given week. This way the study team would be able to identify subjects about whom they were not informed by the primary care taking team.

Patients that were identified to be potential candidates for this study will be screened to evaluate for inclusion/exclusion criteria before approaching the patient for study consent.

Subjects will be informed that their participation is strictly voluntary. They will be assured that the decision to decline participation will have no impact on their care or the perceptions of their providers.

There will be no compensation for participation in this clinical study.

7. Consent Process

Candidate subjects will be informed of the risks and benefits of participation of the study. They will be informed of the study process and demands. They will be given a copy of the informed consent document to review and afforded adequate time to do so. If the elective catheterization procedure (SOC) is scheduled for the upcoming day than the consent will need to be signed before midnight to allow enough time to obtain pre-procedural test as outlined above.

Informed consent will be obtained prior to the right heart catheterization. Consent will be obtained by Study PI, Duke heart center study coordinators who are trained on the study and who have been trained on Informed Consent Process and other key personnel as designated by the PI. Consent will be obtained in the patient's room or the catheterization laboratory holding area. Only after a member of the patients medical care team who is known to the patient approaches them about the study will the study team talk with the patient about this study. A subject is considered enrolled in this clinical study at the time at which the subject and investigator or authorized designee have personally signed and dated the Informed Consent Form.

8. Subject's Capacity to Give Legally Effective Consent:

Subject has to be able to understand the English language and understand the study process including all potential risk and benefits to the patient. Any subject where the study personnel or treatment team has cause for concern regarding the patient's ability to understand the study process or follow the consent process capacity, will be excluded from the study.

9. Study Interventions:

- Regional nerve block under fluoroscopic guidance
- Lab draws
- Vital signs
- Orthostatic vital signs
- 6-minute walk test
- Non-invasive imaging with ultrasound
- Optional: Foley placement

10. Risk/Benefit Assessment:

Procedural risks of splanchnic nerve blocks have been extensively studied. Risks associated with this anesthetic nerve block are uncommon. Mild complications like local pain at injection site, orthostatic hypotension and gastrointestinal dysmotility are time limited and improve with resolution of the anesthetic block. Severe complications like pneumothorax possibly requiring a chest tube, aortic vessel puncture with retroperitoneal bleed or hematothorax and spinal cord injury with possible paralysis. These are very rare since placement of the needle occurs under fluoroscopic guidance.

Other minor risks include (in order of report in literature and experience at Duke):

- Pain at puncture site and intercostal neuralgia
- Gastrointestinal dysmotility including diarrhea, constipation and abdominal cramping as well as nausea
- Bleeding at puncture site

We will perform the splanchnic block for heart failure, which is a new indication. The splanchnic nerve block has not been studied in the setting of this disease. While we don't expect unexpected side effects other than stated above, unexpected side effects cannot be excluded. For safety purposes patients enrolled in this study will remain hospitalized for at least 48 hours (part of enrollment criteria). This way they will be closely monitored while admitted on a cardiology floor/unit.

Anticipated benefits to the patient include improvement in central vascular congestion with a reduction in cardiac preload and pulmonary arterial pressures as well as left sided filling pressures. A reduction in cardiac pressures is also likely to improve symptoms of congestion, including shortness of breath.

Further it is expected that a decongestion of the central veins and interruption of the cardiorenal reflex loop will result in an improvement in renal function as measured by urine output. This will further contribute to the decongestion of the subject's vasculature.

While both of those effects are only temporary, the benefit provided by the brief episode of decongestion can provide lasting symptomatic improvement. Our intervention serves an additional diagnostic purpose by confirming an increased sympathetic tone in the abdominal innervation and could prompt the treatment team to adjust medical therapy to address the increased sympathetic tone and possible benefit on increased splanchnic capacitance.

11. Costs to the Subject:

The study will be at no additional cost to the patient on top of his regular hospitalization for heart failure and elective catheterization.

12. Data Analysis & Statistical Considerations:

Descriptive statistics of continuous outcomes will include sample size, mean, median, standard deviation, minimum and maximum. For categorical outcomes, the number and percentage of subjects in each category will be presented. Statistical comparisons will be made using t-tests for continuous outcomes and chi square or Fisher's exact test (depending on overall event rates) for categorical outcomes. Paired t-tests will be used to compare changes from baseline to post-intervention. All statistical analyses will be performed using SAS for Windows (version 8.2 or higher) or other widely accepted statistical or graphical software. Patient data listings and tabular and graphical presentations of results will be provided. Unless otherwise specified, a two-sided 0.05 level of significance will be used to declare change in pre- and post-procedure variables different.

For power analysis, our primary endpoint is decreased in central venous pressure following nerve blockade. Based on preliminary animal experiments, we anticipate a reduction of CVP of 25%. For a sample size of 16, If the true difference in the experimental and control means is 25%, we will be able to reject the null hypothesis that the population means of the experimental and control groups are equal with probability (power) .90. The Type I error probability associated with this test of this null hypothesis is 0.05.

There is no direct measure of technical success following attempted block of the splanchnic nerves. The location of the splanchnic nerves is estimated biased on human anatomy dissections and established nerve block protocols used by the anesthesiology department. Procedural success to block the splanchnic nerves will be assumed in 70% of the cases based on the experience in splanchnic nerve blocks in patients with intractable cancer.

13. Data & Safety Monitoring:

Due to the experimental nature of this intervention, data will be recorded after each subject completes the intervention for signs of unintended negative effects. These include hypotension, worsening renal function, or clinical deterioration. Additionally, patient's electronic medical data will be clinically screened for any traumatic complications from the nerve block for the first 24 hours postprocedure.

Unanticipated adverse events, which are severe (listed above), will be reported to the IRB within 24 hours. Any other adverse event will be reported to IRB within 10 working days or per IRB requirements. The Principal Investigator will also provide an annual report of any side effects or problems to the IRB during the study renewal process.

Following discharge, the subject's medical record will be monitored for readmission to the Duke hospital for heart failure.

The study related results will be reported to the Duke Translational Research Institute. These would include laboratory tests, imaging studies and clinical tests like 6 minute walk test and dyspnea questionnaire.

- **14. Privacy, Data Storage & Confidentiality** see Section 12 of the e-IRB submission form and complete the questions in that section.
- 1. Data will be obtained by approved study personnel. An enrollment log will also be maintained in Excel Spreadsheet on the Heart Center's S:drive. The subject ID will also be stored on the folder to track patient enrollment and collection of data. Only de-identified data will be available for statistical analysis. All patient identifiers will be removed for database storage, statistical analysis and data reporting. This data will be stored on a study specific folder on the Duke server behind the Duke firewall. The subject ID code will be destroyed after data analysis is completed. Protected health information will not be used for any other purposes than those described in this protocol without obtaining further IRB approval. This information will be used for research purposes only and patients will never be contacted regarding information obtained through chart review. A designated statistician from the DCRI will provide support with statistical analysis.

The adequacy of the Research Data Security Plan (RDSP) will be evaluated and approved by the Cardiology CRU prior to study conduct.

Any publications or presentations that result from this research will not identify any subjects individually, and will present data in aggregate form only.

Gathered data will be stored for at least 6 years.

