This study aims to piggy-back on an elective right heart catheterization (+/- left heart catheterization) in patients admitted for acute decompensated heart failure The right (+/- left heart catheterization) will be part of the subject's standard of clinical care (SOC). Subjects will undergo catheterization of the heart to obtain central cardiac pressure and other cardiac hemodynamic parameters found to be necessary by the primary team. This will occur in the cardiac catheterization lab. Once the SOC catheterization procedure is completed the subject will undergo, as part of this clinical study (CS), a regional nerve block (bilateral splanchnic nerves) while they are in the catheterization lab. This will be performed by an anesthesiologist experienced in splanchnic nerve blocks. Routinely, patient will remain in the catheterization lab for the duration of anesthetic block and will be continuously hemodynamically monitored. Also, prior to elective catheterization procedure and following splanchnic block patients will undergo a number of vital, laboratory and imaging tests, which will be in parts SOC or part of the CS (see Table of Assessments below).

Table of Assessments

Table of Asses	Silicitits						
Required Assessment	<5 Days before procedure	Same day of procedure (<12h before procedure)	Procedure (1-1.5h)	Within 2 hours after Procedure	Day after procedure	48 h after procedure	6 Months after Procedure (±14 days)
Vitals (BP, HR, RR, SpO2)	X (SOC)	X (SOC)	X (SOC)	X (SOC)	X (SOC)	X (SOC)	
Weight	X (SOC)	X (SOC)		X (SOC)	X (SOC)	X (SOC)	
Orthostatic vitals	X (CS)			X (CS)	X (CS)		
Urine output (continuous recording)	X (SOC)	X (SOC+CS)	X (SOC)	X (CS) 3 and 8 hours post procedure	X (SOC+CS)	X (SOC+CS)	
Labs: BMP, pro-BNP, urine sodium,		X (SOC/CS)		X (CS) for pro-BNP and urine sodium	X (SOC) for BMP	X (BMP are SOC, no pro BNP needed)	
Labs (Angiotensin II), Plasma Metanephrines, Vasopressin, Plasma Catecholamines		X (CS)		X (CS)			
Dyspnea Questionnaire		X (CS)	X (CS)	X (CS)	X (CS)	X (CS)	
Six minute walk test	X (CS)	(03)	(03)	(CS)	X (CS)	(CS)	
Impedance and lung fluid content measurement			X (CS)	X (CS)			
Positional Change: Bending Over		X (CS)		X (CS)			
Positional Change: Leg Raise			X (CS)				
Heart rate variability	X (CS)	X (CS)	X (CS)	X (CS)	X (CS)	X (CS)	
Echocardiogram	X (SOC)			X (CS)			
Splanchnic nerve block			X (CS)				
Phone Call**	1 · · · · · · · · · · · · · · · · · · ·						X (CS)

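### The block injects 100–150 micrograms of epinephrine between the two catecholamine draws, so a paired test on epinephrine, metanephrine or an unfractionated total is biased upward

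*Combined protocol and SAP*

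**What the plan says.** Section 4, Procedure, item 2 describes the intervention as "Bilateral splanchnic nerve block performed by an anesthesiologist" and gives the injectate: "Anesthetic solution (1% lidocaine with epinephrine) (1:200.000) will be injected (10-15 ml on each side".

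Section 4, Follow up procedures, sets the blood sampling: "Labs: Angiotensin 2, plasma metanephrines (if on inotropes), plasma catecholamines, vasopressin and urine sodium will be collected immediately before and after the procedure". The Table of Assessments has the row "Labs (Angiotensin II), Plasma Metanephrines, Vasopressin, Plasma Catecholamines", marked twice: in the same-day pre-procedure column and in the column headed "Within 2 hours after Procedure". No later draw is listed. A footnote and the pre-procedure list both restrict metanephrines to subjects on inotropes.

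Section 4 also states that the study is uncontrolled, and it expects the block to last about 1.5 hours. Section 12 gives the general analysis rule: "Paired t-tests will be used to compare changes from baseline to post-intervention", at a two-sided 0.05 level unless specified otherwise.

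The protocol does not mention the injected epinephrine in connection with these assays. It does not say whether epinephrine and norepinephrine (or metanephrine and normetanephrine) will be reported separately. It gives no exact time for the post-block draw.

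**The concern.** Every treated subject is given a measured analyte between the baseline and the follow-up sample. Let δ be the change in the patient's own epinephrine and a the amount added by the injection. The paired difference then estimates δ + a, with a = 0 in the first sample and a > 0 in the second. With no control arm, nothing in the design separates the two terms. The same holds for an unfractionated catecholamine total and, through metabolism of the injected drug, for metanephrine.

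The bias has one direction, upward. If the block lowers the patient's own sympathetic activity, the injected drug works against seeing it in these fractions. The term a also varies between patients with the volume given and the time from injection to draw, so it adds noise as well as bias.

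The protocol already guards against a comparable problem: it moves diuretic doses so that they do not interfere with the intervention. It has no equivalent provision for the epinephrine in its own block solution.

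**Working it through.** The documents state no total epinephrine dose and no expected change in these assays, so there is no planned figure to reproduce.

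**1. Dose (from the documents).** The full stop in the stated ratio is read as a thousands separator.
- Concentration: 1,000,000 micrograms / 200,000 ml = 5 micrograms/ml.
- Volume: 2 sides × 10–15 ml = 20–30 ml.
- Dose: 5 × 20 = 100 micrograms; 5 × 30 = 150 micrograms.

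**2. Time from injection to the second draw (from the documents).** It depends on what is meant by the procedure and on which statement governs.
- Minutes, if the procedure means the block itself.
- 1–1.5 h, if it means the end of monitoring in the catheterization laboratory.
- At most about 1.5 + 2 = 3.5 h, using the outer limit of the table.

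**3. Added plasma epinephrine at the draw (assumptions, not in the documents).** Assume first-order absorption with half-life h, full eventual absorption, and plasma clearance CL of 3–5 L/min. Absorption rate at time t = dose × ln 2 / h × 0.5^(t/h). Added concentration ≈ rate / CL. The approximation assumes that plasma has caught up with the input, so it is not applied to the first minutes after injection.

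Absorption rate in micrograms/min, for 100 / 150 micrograms:

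| Half-life | 1 h | 1.5 h | 3.5 h |
|---|---|---|---|
| 15 min | 0.2888 / 0.4332 | 0.0722 / 0.1083 | 0.0003 / 0.0004 |
| 30 min | 0.5776 / 0.8664 | 0.2888 / 0.4332 | 0.0181 / 0.0271 |
| 60 min | 0.5776 / 0.8664 | 0.4084 / 0.6127 | 0.1021 / 0.1532 |
| 120 min | 0.4084 / 0.6127 | 0.3435 / 0.5152 | 0.1717 / 0.2576 |

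The lowest 100-microgram rate divided by 5 L/min and the highest 150-microgram rate divided by 3 L/min give the range (1 microgram/L = 1,000 pg/ml):
- 1 h: 0.2888/5 = 0.058 to 0.8664/3 = 0.289 micrograms/L, or 58–289 pg/ml.
- 1.5 h: 0.0722/5 = 0.014 to 0.6127/3 = 0.204 micrograms/L, or 14–204 pg/ml.
- 3.5 h: 0.0003/5 ≈ 0 to 0.2576/3 = 0.086 micrograms/L, or 0–86 pg/ml.

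These ranges cover the four half-lives shown. At a fixed time the rate peaks when h = t × ln 2. At 1 h that is about 42 min, giving 150/(60 × 2.718)/3 = 0.307 micrograms/L, slightly above the 289 in the table-based range. The added amount in the pre-block sample is zero under every assumption.

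**4. Can a late draw avoid the problem?** The share not yet absorbed, 0.5^(t/h), is 6–71% at 1 h, 2–59% at 1.5 h and 0–30% at 3.5 h. Contamination may be small at the late end of the window. A draw that late, however, falls after the 1.5 h for which the block is expected to act, so it no longer describes the patient under the block.

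**The case against.** The case against a broad version of this point is good, and most of it stands.

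- A reader might infer that the before/after catecholamine data cannot inform on sympathetic activity at all. The documents do not support that. The injectate contains epinephrine, not norepinephrine. If the external laboratories report fractions, which the plural terms allow, norepinephrine is available from the same samples and is not directly contaminated. Indirect effects of the injected drug on it remain possible.
- These assays appear neither in the Section 2 objectives nor among the Section 4 efficacy endpoints. The paired-test sentence is generic and names no analyte, although by default it covers pre/post variables such as these. No direction of change is stated for them.
- A reader might link the assays to Section 10, which says "Our intervention serves an additional diagnostic purpose by confirming an increased sympathetic tone in the abdominal innervation" and that this could lead the treating team to adjust therapy. Section 10 names no assay, and the haemodynamic response is at least as natural a reading. Section 4 also says these samples may be stored for weeks to months and sent out, so use by the team managing the index admission is implausible.
- A reader might spread the whole dose over 60–90 min and obtain 100/90/5 = 0.22 to 150/60/3 = 0.83 micrograms/L, about 220–830 pg/ml. That is an average during complete absorption, an upper case, and not the level at the draw.
- The documents give no baseline level, so it cannot be shown that a true fall would be hidden or reversed, only that the bias acts in that direction.

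None of this removes the injected epinephrine from the second sample, and nothing in the plan keeps the affected fractions out of a paired test.

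**Conclusion.** The point holds in a limited form. The dose of 100–150 micrograms, its place between the only two draws, and the absence of a control arm follow from the documents. A paired comparison of epinephrine, of an unfractionated total, or of metanephrine in the inotrope subset is therefore biased upward as a measure of endogenous change. Norepinephrine and normetanephrine escape direct contamination.

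The size is uncertain. It rests on the assumed absorption and clearance and on a draw time that the protocol leaves open; it may be a few hundred pg/ml at 1 h and close to nothing at 3.5 h. The effect on metanephrine is not quantified here. The consequence is confined to exploratory assays, because the primary haemodynamic endpoint is not computed from them. The sponsor should correct this, but the trial's main conclusion does not depend on it.

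**What to change.** Using the samples already planned, add to Section 12, with a matching line in Section 4:

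- Fractionated catecholamine and metanephrine results will be obtained.
- The before/after comparison of sympathetic activity will be limited to norepinephrine and, in the inotrope subset, normetanephrine. Patients on a catecholamine infusion will be reported separately.
- Post-block epinephrine, metanephrine and totals will be listed without testing, with a note that they include injected drug.
- The time from injection to the post-block draw will be recorded for each subject and shown with the results.

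The cost is analysis-plan wording, confirmation from the external laboratories that fractions are reported, and one recorded time per subject. The epinephrine fraction is lost as a tested outcome, but its change could not be interpreted as endogenous under the current plan. No change to the block solution is proposed.
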